5.3 End of Study Definition

The start of the trial is defined as first visit for first participant screened. End of trial is defined as the last visit or scheduled procedure shown in the Schedule of Activities for the last participant. Study completion is defined as the final date on which data for the primary endpoint was or is expected to be collected, if this is not the same.

6 STUDY POPULATION

For entry into the study, the following criteria MUST be met.

6.1 Inclusion Criteria

1) Signed Written Informed Consent

- a) Subjects must have signed and dated an IRB/IEC approved written informed consent form in accordance with regulatory and institutional guidelines. This must be obtained before the performance of any protocol related procedures that are not part of normal subject care.
- b) Consent for tumor biopsy samples in subjects with solid tumor
 - i) Subject must consent to allow the acquisition of existing formalin-fixed paraffin-embedded (FFPE) tumor tissue, either a block or unstained slides, for performance of correlative studies. An archival sample is acceptable only if there is not systemic immune-oncology therapy administered after the archival sample is collected. If an archived sample is not available, subject must consent to allow a pre-treatment tumor biopsy. In either case, study personnel must ensure that the tissue block or slides physically exist prior to initiating therapy. Subjects unable to provide an archived tumor sample and who either do not consent to a pre-treatment tumor biopsy or do not have accessible lesions are not eligible. Subjects whose pre-treatment biopsy yields inadequate tissue quantity or quality will not be ineligible on this basis alone.
 - ii) Where possible, the biopsied lesion should be distinct from target lesions being evaluated for radiologic response.
- c) Subjects must be willing and able to comply with scheduled visits, treatment schedule, and laboratory testing.

2) Type of Participant and Target Disease Characteristics

- a) Cohort M1, M2 and C1: Subjects must have histologic or cytologic confirmation of an advanced (metastatic and/or unresectable) malignant solid tumor. Primary CNS malignancy is not allowed.
- b) Cohort C2: Documented refractory or relapsed multiple myeloma
- c) Subjects must be refractory to or have relapsed after standard therapies, or have no known effective treatment. Subjects who refuse or are ineligible for standard therapy will be allowed to enroll provided their refusal/ineligibility is documented in medical records.

d) Subjects cannot have had dose reduced or therapy discontinued due to serious and/or life-threatening IOs-related toxicity (e.g., dose-limiting toxicity in prior study) per Investigator's assessment in consultation with the BMS Medical Monitor.

IO: such as, but not limited to, anti-LAG-3, anti-CTLA-4, anti-PD-1, anti-PD-L1, anti-PD-L2, anti-KIR, anti-CD137, or anti-OX40 antibodies

e) Cohort M1, M2 and C1: Measurable disease according to Response Evaluation Criteria in Solid Tumors version 1.1 (RECIST 1.1)

- Target lesions may be located in a previously irradiated field if there is documented (radiographic) disease progression in that site after the completion of radiation therapy.

f) Cohort C2: Measurable disease at screening within 28 days of treatment assignment, defined as one or more of the following:

- Serum IgG, IgA, or IgM M-protein ≥ 0.5 g/dL
- Urine M-Protein ≥ 200 mg excreted in a 24-hour collection sample
- Involved serum free light chain (sFLC) ≥ 100 mg/L provided the FLC ratio is abnormal

g) Eastern Cooperative Group (ECOG) Performance Status 0-1 ([Appendix 9](#))

h) Cohort M1, M2 and C1: Screening laboratory values must meet the following criteria (using CTCAE v4):

- Neutrophils $\geq 1500/\mu\text{L}$
- Platelet $\geq 100 \times 10^3/\mu\text{L}$
- Hemoglobin ≥ 9.0 g/dL
- Serum creatinine $\leq 1.5 \times \text{ULN}$ or calculated creatinine clearance ≥ 50 mL/min (using the Cockcroft Gault formula)
$$\text{Female CrCl} = \frac{(140 - \text{age in years}) \times \text{weight in kg} \times 0.85}{72 \times \text{serum creatinine in mg/dL}}$$
$$\text{Male CrCl} = \frac{(140 - \text{age in years}) \times \text{weight in kg} \times 1.0}{72 \times \text{serum creatinine in mg/dL}}$$
- PT/INR $\leq 1.5 \times \text{ULN}$ and PTT (aPTT) $\leq 1.5 \times \text{ULN}$
- AST $\leq 3.0 \times \text{ULN}$
- ALT $\leq 3.0 \times \text{ULN}$
- Total Bilirubin $\leq 1.5 \times \text{ULN}$ (except subjects with Gilbert Syndrome who must have a total bilirubin level of $< 3.0 \times \text{ULN}$)
- Albumin > 3.0 g/dL (pancreatic cancer patients only)

i) Cohort C2: Screening laboratory values must meet the following criteria (using CTCAE v4):

- Neutrophils $\geq 750/\mu\text{L}$ (stable off any growth factor within 2 weeks of first study drug administration)
- Platelet $\geq 50 \times 10^3/\mu\text{L}$ (transfusion to achieve this level is not permitted within 2 weeks of first study drug administration)

- iii) Hemoglobin \geq 8.5 g/dL (transfusion to achieve this level is not permitted within 1 week of first study drug administration)
- iv) Serum creatinine \leq 1.5 x ULN or calculated creatinine clearance \geq 40 mL/min (using the Cockcroft Gault formula)
Female CrCl = $\frac{(140 - \text{age in years}) \times \text{weight in kg} \times 0.85}{72 \times \text{serum creatinine in mg/ dL}}$
Male CrCl = $\frac{(140 - \text{age in years}) \times \text{weight in kg} \times 1.0}{72 \times \text{serum creatinine in mg/ dL}}$
- v) PT/INR \leq 1.5 x ULN and PTT (aPTT) \leq 1.5 x ULN
- vi) AST \leq 3.0 x ULN
- vii) ALT \leq 3.0 x ULN
- viii) Total Bilirubin \leq 1.5 x ULN (except subjects with Gilbert Syndrome who must have a total bilirubin level of < 3.0 x ULN)

3) Age and Reproductive Status

- a) Males and Females, \geq ages 20
- b) Women of childbearing potential (WOCBP) must have a negative serum or urine pregnancy test (minimum sensitivity 25 IU/L or equivalent units of HCG) within 1 day prior to the start of study treatment.
- c) Women must not be breastfeeding (Even if breastfeeding is suspended, participation in the study is not allowed)
- d) Women of childbearing potential (WOCBP) must agree to follow instructions for method(s) of contraception for the duration of treatment with study treatment(s) and for a total of 5 months post-treatment completion.
- e) Males who are sexually active with WOCBP must agree to follow instructions for method(s) of contraception ([Appendix 4](#)) for the duration of treatment with study treatment(s) and for a total of 7 months post-treatment completion. In addition, male participants must be willing to refrain from sperm donation during this time.
- f) Azoospermic males are exempt from contraceptive requirements. WOCBP who are continuously not heterosexually active are also exempt from contraceptive requirements, and still must undergo pregnancy testing as described in this section.

Investigators shall counsel WOCBP, and male participants who are sexually active with WOCBP, on the importance of pregnancy prevention and the implications of an unexpected pregnancy. Investigators shall advise on the use of highly effective methods of contraception ([Appendix 4](#)) which have a failure rate of $< 1\%$ when used consistently and correctly.

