2 SCHEDULE OF ACTIVITIES

Table 2-1: Screening Procedural Outline (CA025001)		
Procedure	Screening Visit Within 28 days prior to treatment assignment	Notes
Eligibility Assessments		
Informed Consent	X	A participant is considered enrolled only when a protocol specific informed consent is signed.
Inclusion/Exclusion Criteria	X	
Medical History	X	Include any toxicities or allergy related to previous treatments.
Baseline Tumor Assessment	X	
Prior/Concomitant Medications	X	
Safety Assessments		
Physical Examination (PE)	X	If the screening PE is performed within 1 day prior to dosing on Day 1 then a single exam may count as both the screening and pre-dose evaluation.
Physical Measurements	X	Includes height and weight.
ECOG P.S.	X	
Assessment of Signs and Symptoms	X	
Vital Signs	X	Includes body temperature, respiratory rate, and blood pressure and heart rate (sitting or supine). Blood pressure and heart rate should be measured after the participant has been resting quietly for at least 5 minutes. Pulse oximetry is performed at rest and after exertion prior to nivolumab dosing at each dosing visit only for the combination cohorts. Refer to Section 9.4.2
Electrocardiogram (ECGs)	X	ECGs should be recorded after the participant has been supine for at least 5 minutes.

Table 2-1: Screening Procedural Outline (CA025001)

Procedure	Screening Visit Within 28 days prior to treatment assignment	Notes
Laboratory Tests	X	Hematology: CBC with differential, platelets, hemoglobin, hematocrit, RBC Chemistry: CK, AST, ALT, alkaline phosphatase, bilirubin (direct and total), BUN, calcium, chloride, creatinine, glucose, cholinesterase, LDH, phosphorus, potassium, sodium, albumin, amylase, lipase, thyroid panel (TSH, Free T3 and Free T4), PT/INR, PTT (aPTT) and Troponins Urinalysis: Glucose, Protein, Blood
Serology	X	Includes hepatitis C antibody, hepatitis B surface antigen/hepatitis B core antibody, and Interferon-Gamma Release Assays (e.g. Quantiferon test).
Pregnancy Test	X	For WOCBP only.
Follicle Stimulating Hormone (FSH)	X	Women only. Refer to Appendix 4 .
Baseline Tumor Assessment		
For Solid tumor : Tumor Assessments	X	Refer to Section 9.1.1
For Multiple Myeloma		Refer to Section 9.1.2
Myeloma Urine and Serum Lab tests (SPEP/UPEP/sFLC)	X	
Bone Marrow Aspiration/Biopsy	X	Refer to Table 9.1.2.1-1
Skeletal survey	X	

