Documentation of extramedullary soft tissue plasmacytomas, if clinically indicated	X	Perform CT or MRI at screening if clinically indicated or if patient had a previous extramedullary or bone plasmacytoma.
[REDACTED]	[REDACTED]	[REDACTED]

Table 2-1: Screening Procedural Outline (CA025001)

Procedure	Screening Visit Within 28 days prior to treatment assignment	Notes
Adverse Event Reporting		
Monitor for Serious Adverse Events	X	All SAEs must be collected from the date of participant's written consent

Table 2-2: Treatment Phase Procedural Outline (CA025001)

Procedure	Cycle ^a 1				Cycle 2~	EOT ^b	Follow-up Period 28 days and 100 days post-last dose	Notes
	D 1	D 2	D 4	D 8				
Safety Assessments								
Physical Examination (PE)	X			X	X	X	X	
ECOG P.S.	X				X	X	X	
Physical Measurements ^c	X				X	X	X	Weight only Within 72 hours prior to dosing.
Vital Signs	X			X	X	X	X	See note in screening procedures and Section 9.4.2 . Cohort C1, C2: measure Pulse oximetry at rest and after exertion prior to nivolumab dosing
Electrocardiogram (ECGs) Refer to the DM ECG Study Guidelines	X				C2D1	X		See note in screening procedures and Section 9.4.3 . Pre dose and within 1 hour of completion of cabiralizumab dosing on C1D1 and C2D1
Laboratory Tests ^c	X			X	X	X	X	See note in screening procedures and Section 9.4.4 . Pre-dose on Day 1 on each cycle. Within 72 hours prior to dosing.
Pregnancy Test ^c	X				X	X	X	Every 2 cycles D1 within 72 hours prior to dosing
Adverse Event Reporting	X							

Table 2-2: Treatment Phase Procedural Outline (CA025001)

Procedure	Cycle ^a 1				Cycle 2~	EOT ^b	Follow-up Period 28 days and 100 days post-last dose	Notes		
	D 1	D 2	D 4	D 8	D 1					
Monitor for Non-Serious Adverse Events	X									
Monitor for Serious Adverse Events	X							All SAEs must be collected from the date of participant's written consent until 100 days of discontinuation of dosing		
Concomitant Medications Collection	X									
Pharmacokinetic (PK)/ADA Assessments										
Serial Blood PK Sampling	X	X	X	X	X ^d	X	X	See Section 9.5.		
ADA sampling	X				X ^e	X	X	See Section 9.5.		
Efficacy Assessments										
Tumor Assessments (for Solid tumor)	X					X ^f	Every 8 weeks (\pm 7 days) for first 48 weeks, then every 12 weeks (\pm 7 days) thereafter See Section 9.1.1			
For Multiple Myeloma										

Table 2-2: Treatment Phase Procedural Outline (CA025001)

Procedure	Cycle ^a 1				Cycle 2~ D 1	EOT ^b	Follow-up Period 28 days and 100 days post-last dose	Notes				

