	D 1	D 2	D 4	D 8								
Myeloma Urine and Serum Lab tests (SPEP/UPEP/sFLC)	X				X ^f		Day 1 on every 2 cycles starting from C3D1					
Bone Marrow Aspiration/Biopsy	For confirmation of CR/sCR if applicable or, if clinically indicated at time of suspected disease progression											
Skeletal survey	If clinically indicated											
Documentation of extramedullary soft tissue plasmacytomas, if clinically indicated	As clinically indicated and at the time of CR/sCR assessments											
Flow Cytometry	For confirmation of CR/sCR if applicable or, if clinically indicated at time of suspected disease progression											
Subsequent Treatment (Anti-cancer)					X							
Survival Status					X							
Clinical Drug Supplies												
Study Drug Administration ^g	X				X		Those supplied by BMS					

^a Each cycle is 14-days.

^b End of treatment (EOT) is defined as the visit where the decision is made to discontinue the participant from treatment.

^c Physical measurements and laboratory tests do not need to be repeated if completed within the last 72 hours

^d Cycles 2-9, 13, 21

^e Cycles 2, 3, 5, 9, 13, 21

^f Only participants who have not discontinued study treatment for progressive disease.

^g Every 14 days (2days), subjects may be dosed no less than 12 days from the previous dose.

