5 STUDY DESIGN

5.1 Overall Design

This study is a Phase 1, open-label, dose escalation study to evaluate the safety, tolerability, PK, and PD and preliminary anti-tumor activity of cabiralizumab as monotherapy in subjects with advanced solid tumor. In addition, the study will evaluate the safety profile, PK, PD and preliminary anti-tumor activity of cabiralizumab in combination with nivolumab in subjects with advanced solid tumors and hematologic malignancies.

For the monotherapy cohorts of the study, cabiralizumab will be given on Day 1 of each 14-day treatment cycle until the progression of disease, discontinuation of toxicity, withdrawal of consent or study closure. For the combination cohorts of the study, cabiralizumab and nivolumab will be given on Day 1 of each 14-day treatment cycle until the progression of disease, discontinuation of toxicity, withdrawal of consent or study closure. Nivolumab will be administered as an IV infusion over 30 minutes, and then cabiralizumab will be administered as an IV infusion over 30 minutes.

This study consists of 2 planned cabiralizumab monotherapy cohorts (M1: 2 mg/kg and M2: 4 mg/kg) and 2 cohorts of cabiralizumab in combination with nivolumab (C1: 4 mg/kg

cabiralizumab and 3 mg/kg nivolumab in subjects with solid tumor and C2: 4 mg/kg cabiralizumab and 3 mg/kg nivolumab in subjects with hematologic malignancies).

The study will consist of 3 periods: Screening, Treatment and Follow-up. The study will end after the last subject completes the last visit.

Screening begins by establishing the subject's initial eligibility and signing of the informed consent form (ICF). Subjects must have treatment assignment within 28 days after signing the informed consent.

The Treatment Phase begins when the treatment cohort is assigned to the subjects. The subject will be assigned to the open cohort (M1, M2, C1, or C2) at the timing of the treatment assignment. First dose should be started within 3 days of treatment assignment. The subjects will be required to be hospitalized for safety evaluation at least for 8 days from the first dose. The subjects can be discharged at the investigator's discretion at Day 8.

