9 STUDY ASSESSMENTS AND PROCEDURES

- Study procedures and timing are summarized in the Schedule of Activities.
- Protocol waivers or exemptions are not allowed.
- All immediate safety concerns must be discussed with the Sponsor immediately upon occurrence or awareness to determine if the participant should continue or discontinue treatment.
- Adherence to the study design requirements, including those specified in the Schedule of Activities, is essential and required for study conduct.
- All screening evaluations must be completed and reviewed to confirm that potential participants meet all eligibility criteria before treatment assignment. The investigator will maintain a screening log to record details of all participants screened and to confirm eligibility or record reasons for screening failure, as applicable.
- Procedures conducted as part of the participant's routine clinical management (e.g., blood count) and obtained before signing of informed consent may be utilized for screening or baseline purposes provided the procedure meets the protocol-defined criteria and has been performed within the timeframe defined in the Schedule of Activities.

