9.4.4 Clinical Safety Laboratory Assessments

- Investigators must document their review of each laboratory safety report.
- A local laboratory will perform the analyses and will provide reference ranges for these tests.
- Results of clinical laboratory tests performed at Day 1 on each cycle must be available prior to dosing (unless obtaining assessment results are not possible due to local laboratory feasibility).

Hematology

Hemoglobin

Hematocrit

CBC including differential

Platelet count

RBC

Serum Chemistry	
Aspartate aminotransferase (AST)	Albumin
Alanine aminotransferase (ALT)	Sodium
Total bilirubin	Potassium
Direct bilirubin	Chloride
Alkaline phosphatase	Calcium
Lactate dehydrogenase (LDH)	Phosphorus
Creatinine	Creatine kinase
Blood Urea Nitrogen (BUN)	Tropoains
Glucose	Amylase
Cholinesterase	Lipase
	TSH
	FT3, FT4
	PT/INR
	PTT(aPTT)
Urinalysis	
Protein	
Glucose	
Blood	
Serology	
Serum for hepatitis C antibody, hepatitis B surface antigen, HBc antibody, and Interferon-Gamma Release Assays (e.g. Quantiferon test) (screening only)	
Other Analyses	
Pregnancy test (WOCBP only: screening, predose).	
Follicle stimulating hormone (FSH) (screening only for women only) if required	

If CK elevation is clinically significant, obtain troponins (cardiac), CK isoenzymes, aldolase, and ECG; repeat CK and these additional tests within 48 hours or other interval as clinically indicated, until resolved or stable. If either AST or ALT is elevated, obtain total serum bilirubin, alkaline phosphatase; repeat within 48 hours or other interval, as clinically indicated, until resolved or stable. Additional tests may be obtained at any time, if clinically indicated. If a patient is being followed for a tumor marker (e.g. CA-125, or others), a sample for the tumor marker should be obtained at screening and every other cycle, or if clinically indicated during the study.

9.4.5 *Optional Liver Biopsy*

Optional liver biopsy may be performed at the discretion of the Investigator with an agreement with the Sponsor in the presence of significant liver enzyme elevations. It is performed to understand whether or not such elevations are clinically/pathologically relevant.

9.4.6 *Imaging Safety Assessment*

Any incidental findings of potential clinical relevance that are not directly associated with the objectives of the protocol should be evaluated and handled by the Study Investigator as per standard medical/clinical judgment.

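### The schedule allows a 72-hour-old pregnancy test at the first dose, where inclusion criterion 3b allows only 1 day

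*Protocol*

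**What the plan says.** - **Protocol Section 6.1, inclusion 3b.** A WOCBP needs a negative serum or urine test "within 1 day prior to the start of study treatment".
- **Protocol Section 2, Table 2-2 (treatment phase).** The pregnancy test row has an X in the Cycle 1 D1 column. Its note reads "Every 2 cycles D1 within 72 hours prior to dosing". The row label carries footnote c: "Physical measurements and laboratory tests do not need to be repeated if completed within the last 72 hours".
- **Protocol Section 2, Table 2-1 (screening).** The pregnancy test is listed in the 28-day screening window, with a note that it applies to WOCBP only.
- **Protocol Section 9.4.4.** The entry is "Pregnancy test (WOCBP only: screening, predose", with no window in hours or days.
- **Protocol Section 9.** "Study procedures and timing are summarized in the Schedule of Activities". The same list says "Protocol waivers or exemptions are not allowed".
- **Protocol Section 5.1.** "The Treatment Phase begins when the treatment cohort is assigned to the subjects", and up to 3 days may then pass before the first dose.

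**The concern.** Two parts of the current protocol give different maximum ages for the same test before the same dose, and the looser figure is in the table that sites use to plan visits. The test is the last check for pregnancy before the first exposure to an investigational antibody. If a coordinator books C1D1 from Table 2-2, a WOCBP could be dosed on a result that 3b does not accept. That would be an eligibility deviation under a protocol that allows no waivers, and it would weaken a fetal-safety safeguard. No endpoint, sample size or analysis depends on this.

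**Working it through.** There is no planned statistic to reproduce. The check compares two time windows and asks whether any text reconciles them.

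**1. Does Table 2-2 govern the first dose?** Yes. Section 5.1 starts the treatment phase at cohort assignment, which comes before dosing, so C1D1 falls inside the phase that Table 2-2 covers. The row is marked in the C1 D1 column. No sentence in the row, the footnotes or the text exempts the first dose.

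**2. How far apart are the windows?** Inputs: 72 hours (Table 2-2 row note and footnote c) and 1 day (inclusion 3b). The protocol does not define 1 day, so both plausible readings are shown.

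| Reading of 1 day | Oldest test 3b accepts | Oldest test Table 2-2 accepts | Ages that pass the table and fail 3b |
|---|---|---|---|
| 24 hours | 24 h | 72 h | over 24 h, up to 72 h (72 − 24 = 48 h wide) |
| Preceding calendar day | under 48 h | 72 h | 48 h to 72 h (72 − 48 = 24 h wide) |

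A test 48 to 72 hours old therefore meets the schedule and fails eligibility under either reading.

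**3. Can a site get there by following the protocol?** Yes. Section 9 requires screening evaluations to be complete and eligibility confirmed before assignment. Section 6.4.1 judges inclusion on the most recent result before assignment. Section 5.1 then permits up to 3 days (3 × 24 = 72 h) until the first dose. A woman tested just before assignment and dosed more than 2 days later can still be inside the Table 2-2 window. The schedule would tell the site that no repeat is needed when 3b requires one.

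**4. Does other text supply the 1-day rule?** No. Table 2-1 gives only the screening window, and Section 9.4.4 gives none. Neither conflicts with 3b, but neither would alert a site to it.

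**5. How often would it happen?** The documents give neither the number of WOCBP nor planned test times, so no frequency can be estimated.

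**The case against.** The strongest reply is that the texts do not contradict each other. Criterion 3b is stricter, and a test that meets it also meets the table. Section 7.2 makes eligibility a condition of dosing, Section 6.2 closes by insisting that every criterion be met, and Section 9 forbids waivers and describes the schedule only as a summary. Harm requires a site to overlook a criterion that it must verify for each woman. All of that is right: the safeguard exists and 3b governs. It does not make the window printed for C1D1 correct.

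The row note can also be read as the rule for repeat testing, with 3b controlling at entry. That is a sensible reading and probably the intended one, but the table does not say so and the X sits under C1 D1.

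Footnote c names physical measurements and laboratory tests, while the pregnancy test has its own row. This weakens the footnote as support. However, the marker is attached to the pregnancy row, Section 9.4.4 lists the test among the laboratory assessments, and the row's own note gives 72 hours independently.

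Table 2-1 has a first-dose note for the physical examination ("If the screening PE is performed within 1 day prior to dosing on Day 1 then a single exam may count as both"), but that is an allowance to use one examination twice. It is weak evidence that the pregnancy row should have a similar note, and the point does not rest on it.

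Finally, the protocol accepts a 72-hour window later in treatment, with testing every 2 cycles (2 × 14 = 28 days), and requires contraception. A negative test 3 days old is therefore not a gross lapse, which limits the seriousness of the point.

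**Conclusion.** The point holds. The Table 2-2 pregnancy row, as written, states a looser window at C1D1 than inclusion 3b. The excess is 48 hours if 1 day means 24 hours, and at least 24 hours if it means the preceding calendar day. The realistic consequence is an occasional eligibility deviation on a fetal-safety check, limited to WOCBP at first dose. The chosen windows (1 day at entry, 72 hours on treatment) are not in dispute; the defect is that the schedule does not carry the first of them. It should be corrected because the check concerns safety and the correction is small. The conclusion rests on the current text alone and assumes only that sites use the schedule for visit timing, as Section 9 directs.

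**What to change.** Make two edits in Table 2-2.

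1. Replace the pregnancy row note with: *C1D1: negative result no more than 1 day before first dose, per inclusion 3b; later cycles: every 2 cycles, no more than 72 hours before dosing.*
2. Add to footnote c: *Does not apply to the C1D1 pregnancy test.*

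In the same amendment, state in 3b whether 1 day means 24 hours or the preceding calendar day; otherwise the new note inherits that ambiguity.

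The cost is one row note, one footnote qualifier and a short definition, plus an occasional repeat urine or serum test for a woman tested more than 1 day before C1D1. Testing at later cycles is unchanged.
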